4.5 Demographics and Anthropometric Information and Baseline Characteristics

The demographic and anthropometric variables (age, race, ethnicity, sex, height, body weight, body mass index [BMI] will be summarized for all patient by cohort, treatment and overall.

Demographic and anthropometric variables (age, sex, ethnicity, race, height, weight, and BMI) will be listed by patient for the SAF.

Age, height, BMI, weight will be summarized using the n, mean, SD, minimum, median, and maximum. The count and percentage will be computed for sex, race, and ethnicity.

A by-patient listing of history of substance abuse and history of RA and related surgical history will be provided.

4.6 Medical and Surgical History

Medical and surgical history will be coded using Medical Dictionary for Regulatory Activities (MedDRA[®]), Version 25.0 and assigned to a System Organ Class (SOC) and Preferred Term (PT).

A by-patient listing for medical and surgical history including visit, description of the disease/procedure, Medical Dictionary for Regulatory Activities (MedDRA) System Organ Class (SOC), MedDRA preferred term (PT), start date, and stop date (or ongoing if applicable) will be provided, and summarized for the SAF.

4.7 **Prior and Concomitant Medications**

Prior and Concomitant Medication:

Medications will be considered as prior if it is started and stopped prior to the first dose of study drug.

Medications will be considered as concomitant if they are taken after first dosing (including medications that started prior to dosing and continued after)

Prior and concomitant medication will be coded according to the World Health Organization Drug Dictionary (WHO-DD) latest version.

By-patient listings of prior and concomitant medications including the following information: reported name, PT, the route of administration, dose, frequency, start date/time, duration, and indication will be provided, by WHO DD terms for the SAF.

Prior Medications and concomitant medication will be summarized by WHO DD terms for the SAF.

4.8 Treatment Exposure and Compliance

4.8.1 Treatment Exposure

A by-patient listing of patient exposure to study drug will be generated. The listing will include date and time of administration.

4.8.2 Compliance

A by-patient listing of treatment compliance will be provided.

Overall Treatment Compliance (%) will be defined as percentage of total dose taken during the study divided by the expected total dose in mg.

4.9 Analysis Supporting Primary Objective(s)

Not Applicable

4.10 Analysis Supporting Secondary Objective(s)

Not Applicable

4.11 Efficacy Evaluation

Not Applicable

4.12 Pharmacokinetic Analysis, Concentration, and Parameter TFLs, and Statistical Analysis of Pharmacokinetic Parameters for Final Analysis

4.12.1 Pharmacokinetic Concentrations

Concentration Listings:

Pharmacokinetic Plasma concentration data for TCK-276 and TEI-W00595, will be listed by cohort/treatment/Day and patient for the PKAS. Concentration listings will include nominal PK sampling time, actual sampling times relative to dose administration, deviation from nominal time, and percent deviation from nominal time, and concentrations. Plasma concentrations below the lower limit of quantification (LLOQ) will be presented as below the limit of quantification (BLQ) in the listings and the LLOQ value presented as a footnote. Missing PK samples will be reported as no sample (NS) or not reportable (NR) as appropriate and considered excluded from PK analysis.

Concentration Summary Tables:

Source data as reported from the laboratory will be used for calculation of concentration summary statistics. Tabular summaries for concentration-time data will report N (number of patients in PKAS), n (number of patients with non-missing values), and n(BLQ) (the number of patients with BLQ samples).

Concentration for TCK-276 and TEI-W00595 will be summarized by cohort/treatment/Day, and nominal timepoint for the PKAS. The following descriptive statistics will be presented for plasma concentrations obtained at each nominal time point: N, n, n(BLQ), arithmetic mean, SD, coefficient of variation (CV%), geometric mean, geometric CV% (calculated as: $gCV\% = SQRT(e^{s^2}-1)*100$; where s is the SD of the log-transformed values), median, minimum, and maximum values.

For summary concentration tables, all BLQs will be considered zero, and the number of BLQs and quantifiable concentrations at each scheduled time point will be reported. Summary Statistics will not be calculated if quantifiable concentrations at a scheduled time point is <3 and will be reported as not calculated (NC).

The rules followed for calculation and presentation of concentration data with regards to the number of decimal places/significant digits for the listings of patient level concentrations and summary tables of concentration are as follows:

Concentration Listings and Tables	Rounding
Individual concentrations (Listings)	n s f. as supplied by bioanalytical laboratory
Minimum and Maximum	n s f. as supplied by bioanalytical laboratory
Mean/SD/Median/Geomean	3 s.f.
CV%/gCV%	1 d.p.
N/n	Whole number

s f = significant figures, d.p. = decimal place

For the final plasma concentration PK summary tables and figures, if the 0.25 and 0.5 h samples are collected outside \pm 5 minutes time window, the concentration will be flagged and not included in the concentration summary tables and mean concentration-time plots. For 1 to 48 h sample, if the sample is collected outside 10% time deviation of the scheduled time or outside \pm 30 minutes time window, it will be flagged and not included in the concentration summary tables and mean

concentration-time plots. For 72 h sample, if the sample is collected outside \pm 60 minutes time window, it will be flagged and not included in the concentration summary tables and mean concentration-time plots.

Concentration Figures:

For arithmetic mean linear/linear graphs, all BLQ values will be substituted with zero for calculation of arithmetic mean. The arithmetic mean will not be calculated if quantifiable concentrations at a scheduled time point is <3 and will not be plotted in Figures. For log/linear graphs the log transformed arithmetic mean will be displayed (this should not include zero).

For individual linear/linear and log/linear graphs, all BLQ values will be substituted as follows:

- BLQs at the beginning of a patient profile (i.e., before the first incidence of a measurable concentration) will be assigned to zero. When using log/linear scale, these timepoints will be considered missing.
- BLQs at the end of a patient profile (i.e., after the last incidence of a measurable concentration) will be set to missing.
- Single BLQs which fall between two measurable concentrations will be set to missing.
- Consecutive BLQs which fall between measurable concentrations will be set to missing.
- If there are quantifiable concentrations following consecutive BLQs in the apparent terminal phase, these values will be evaluated. If these values are considered to be anomalous, they will be set to missing.

To visualize patient-level concentrations and the comparison between cohort/treatment, the descriptive PK graphs listed below will be generated.

- Figure x.x.x: Individual patient profiles for TCK-276 and TEI-W00595 Plasma Concentration Time Data for Day 1 and Day 7 dosing by Dose (Linear Scale and Semi-Logarithmic Scale) (PKAS) [4 profiles for every individual, Day 1 parent, Day 7 parent, Day 1 metabolite, Day 7 metabolite)]
- Figure x.x.x : Overlaid individual patient profiles for TCK-276 Plasma Concentration Time Data for Day 1 and Day 7 dosing by Dose (Linear Scale and Semi-Logarithmic Scale) (PKAS) [Plots for Dose 1 Days 1-2, Dose 7 Days 7-10)]
- Figure x.x.x : Overlaid individual patient profiles for TEI-W00595 Plasma Concentration Time Data for Day 1 and Day 7 dosing by Dose (Linear Scale and Semi-Logarithmic Scale) (PKAS) [Plots with Dose 1 Days 1-2, Dose 7 Days 7-10]
- Figure x.x.x: Overlaid individual patient profiles for TCK-276 Plasma Trough Concentration Time Data by Dose – (Linear Scale and Semi-Logarithmic Scale) (PKAS) [Plots for Day 2 – Day 8]
- Figure x.x.x: Overlaid individual patient profiles for TEI-W00595 Plasma Trough Concentration Time Data by Dose – (Linear Scale and Semi-Logarithmic Scale) (PKAS) [Plots for Day 2 – Day 8]

- Figure x.x.x : Mean (+ SD) TCK-276 Trough Plasma Concentration Time Data (Linear Scale and Semi-Logarithmic Scale) (PKAS) [*Plots for Day 2 Day 8 for all doses* on one plot)
- Figure x.x.x : Mean (+ SD) TEI-W00595 Trough Plasma Concentration Time Data (Linear Scale and Semi-Logarithmic Scale) (PKAS) [*Plots for Day 2 Day 8* for all doses *on one plot*)
- Figure x.x.x : Mean (+ SD) TCK-276 Plasma Concentration Time Data for Day 1 and Day 7 by Dose (Linear Scale and Semi-Logarithmic Scale) (PKAS) [Plots for Day 1 all doses, Day 7 all doses and Plots for from Day 1 to Day 7)
- Figure x.x.x : Mean (+ SD) TEI-W00595 Plasma Concentration Time Data for Day 1 and Day 7 by Dose (Linear Scale and Semi-Logarithmic Scale) (PKAS) [Plots for Day 1 all doses, Day 7 all doses and Plots for from Day 1 to Day 7)
- Figure x.x.x : Mean (+ SD) TCK-276 Plasma Concentration Time Data for Day 1 and Day 7 by cohort (Linear Scale and Semi-Logarithmic Scale) (PKAS) [*Plots for Day 1; Day 7; Day 1, Day 7 and trough day 3-6*)
- Figure x.x.x : Mean (+ SD) TEI-W00595 Plasma Concentration Time Data for Day 1 and Day 7 by cohort (Linear Scale and Semi-Logarithmic Scale) (PKAS) [Plots for Day 1; Day 7; Day 1, Day 7 and trough day 3-6)

Figures will be generated in black and white using unique line style and marker for each plot in the graph. For all PK concentration-time plots, linear scale will be used for x-axis (i.e. do not use an ordinal scale).

4.12.2 Pharmacokinetic Parameters

PK parameters will be provided by CPMS group. PK parameters will be calculated by NCA methods from the concentration-time data using Phoenix[®] WinNonlin[®] Version 8.3 or higher following these guidelines:

- Actual time from dose will be used in the calculation of all derived pharmacokinetic parameters, except when parameters are calculated for safety/dose escalation meetings when nominal times may be used to calculate PK parameters.
- There will be no imputation of missing data.
- Handling of BLQ samples for derivation of plasma PK parameters after multiple dose administration
 - BLQs for Day 1 at the beginning of a patient profile (i.e., before the first incidence of a measurable concentration) will be assigned to zero
 - BLQs on subsequent dosing days, and BLQs in the absorption phase will be substituted by zero before the calculation of the PK parameters
 - BLQ values between non-BLQ concentrations will be considered missing
 - \circ Terminal BLQs (at the end of patient profile) will be set to missing
- If urinary concentration is BLQ or if urine volume is not collected, amount of unchanged drug recovered in urine (A_e) will be defined as NC

Pharmacokinetic parameters will be estimated according to the guidelines presented in Table 4-1.

Parameter **Guideline for Derivation** C_{max}, t_{max}, C_{trough}, Obtained directly from the observed concentration-time data. If multiple t_{max} values are observed the earliest value will be reported. AUC_{0-t} The AUC from zero time (pre-dose) to the time of last quantifiable concentration will be calculated by the linear trapezoidal linear interpolation rule. The AUC_{0-t} is the sum of areas up to the time of the last quantifiable sample: $AUC_{0-t} = \int_0^t C_{last} * dt$ where C_{last} is the last observed quantifiable concentration. AUC_{tau} The AUC over the dosing interval (24 hours) will be determined for multiple dose studies using the trapezoidal rule, as stated above. The area from zero time extrapolated to infinite time will be calculated as follows: AUC_{0-inf} $AUC_{0-inf} = AUC_{0-t} + \frac{C_{\text{last}}}{\lambda_z}$ where Clast is the last observed quantifiable concentration. The percentage of AUC_{0-inf} obtained by extrapolation will be calculated as follows: %AUCex $\% AUC_{ex} = \frac{AUC_{0.inf} - AUC_{0.inf}}{AUC_{0.inf}} \times 100 .$ The apparent terminal phase rate-constant (λz) will be estimated by linear 1. λz and $t^{1/2}$ regression of concentration versus time data presented in a log-linear scale. Data are primarily monotonically decreasing in magnitude and are 2. representative of the actual decline in the log concentration-time curve. Only those data points that are judged to describe the terminal log-linear 3. decline will be used in the regression. 4. A minimum number of three data points in the terminal phase will be used in calculating λz with the line of regression starting at any post-C_{max} data point (C_{max} should not be part of the regression slope). Lambda z (λ_z) and other λ_z -related parameters (i.e. t¹/₂, AUC_{0-inf}, CL/F, MRT_{0-inf}, and V_z/F) will be flagged in listings and excluded accordingly from summary tables and statistical analysis of PK parameters, if the adjusted correlation coefficient (R^2 adjusted) is <0.8, and/or the interval used to determine λz is <1.3 times the half-life and/or %AUC_{ex} is >30%, unless otherwise determined by PK Scientist's best knowledge and judgment or if

Table 4-1 Pharmacokinetic Parameter and Estimation

	instructed by the Sponsor.		
	6. The $t^{1/2}$ will be calculated as follows:		
	$t^{1/2} = \ln 2/\lambda z = 0.693/\lambda z$		
	7. Data points may be dropped from the linear regression if the PK Scientist		
	considers the reported values to be anomalous. Any data points so designated		
	should remain in the listings with a footnote and be identified in the study report		
	with a rationale for exclusion.		
CI /F	Apparent clearance after 1 st dose will be calculated as follows:		
CL/I	$CL/F = \frac{Dose}{AUC_{0-inf}}$		
	Apparent clearance (CL/F) following oral dosing will be calculated similarly for Day 7 where AUC_{tau} will be the denominator, assuming steady state has been achieved then.		

Parameter	Guideline for Derivation	
MRT _{last}	MRT _{last} will be calculated as follows: MRT _{last} = AUMC _{last} /AUC _{last} (Day 1 only)	
MRT _{0-inf}	MRT _{0-inf} will be calculated as follows:	
	Day 1: AUMC _{0-inf} /AUC _{0-inf}	
	Day 7: $(AUMC_{tau} + \tau^*(AUC_{0-inf} - AUC_{tau})) / AUC_{tau}$	
	Where AUMC is the area under the moments curve and τ is the dosing interval.	
V _z /F	Volume of distribution at terminal phase on Day 1 will be calculated as follows:	
	$V_z/F = \frac{Dose}{\lambda_z \times AUC_{0-inf}} = (CL/F)/\lambda_z$	
	Likewise, if derived for Day 7 or steady, AUC_{tau} will be used.	
CLr	Renal clearance will be calculated from the ratio of the appropriate values for urinary recovery and area under the concentration-time curve, where x will be 24 (Day 1) and 72 (Day 7) hours:	
	$CL_r = \frac{Ae_{(0-x)}}{AUC_{(0-x)}}$	
R _{acc}	Accumulation ratio, calculated from comparison of single dose (Day 1) and steady state (Day 7) data:	
	$R_{acc}(AUC_{tau}) = \frac{Steady \ state \ AUC_{tau}}{Single \ dose \ AUC_{tau}}$	
	$R_{acc}(C_{max}) = Steady \ state \ C_{max} / Single \ dose \ C_{max}$	
A _e	Amount of unchanged drug recovered in urine is calculated as	
	$A_e = Urine \ drug \ concentration \ * \ urine \ volume$	
	This is calculated for each urine collection interval and then summed for the cumulative A_{e} .	
Fe%	The percent of drug recovered in urine is calculated as	
	$F_e = 100 * A_e/Dose$	
	This is calculated for each urine collection interval and then summed for the cumulative $F_e\%$.	
MR for AUC	Metabolite molar ratio for Day 1 and Day 7 will be calculated as	
	MR for $AUC_{0-inf} = (AUC_{0-inf} metabolite/AUC_{0-inf} parent) * (MW parent/MW metabolite)$	
	Similarly, metabolite molar ratios will be collected for other AUCs defined earlier in this SAP.	
	Metabolite molar ratios will be calculated based on molecular weight of parent, TCK-276 and for metabolite TEI-W00595.	

Parameter	Guideline for Derivation
MR for C _{max}	Metabolite molar ratio for Day 1 and Day 7 will be calculated as MR for $C_{max} = (C_{max} metabolite/ C_{max} parent) * (MW parent/MW metabolite)$
	Metabolite molar ratios will be calculated based on molecular weight of parent, TCK-276 and for metabolite TEI-W00595.
DNC _{max} , DNAUC _{0-t} , DNAUC _{0-inf} , DNAUC _{tau}	Parameter value divided by dose

PK Parameters Listings:

PK parameters will be listed by patient for the PK Population. PK parameters that will be flagged and/or excluded from summary tables and statistical analyses of PK parameters will be flagged and footnoted with the reason for flagging/exclusion.

PK Parameter Summary Tables:

Biostatistics group will consider the derived PK parameters as source data and will use this data without rounding for calculation of PK parameters summary statistics tables.

PK parameters will be summarized by cohort/treatment and Day for the PK population. Tabular summaries for PK parameters will report N (number of patients who received treatment) and n (number of patients with non-missing PK parameter). Descriptive statistics for calculated PK parameters will include N, n, arithmetic mean, SD, CV%, geometric mean, gCV%, median, minimum, and maximum values. For t_{max}, only N, n, arithmetic mean, SD, CV%, median, minimum, and maximum values will be presented. No descriptive statistics will be determined when fewer than three individual PK parameters are available.

The rules followed for presentation of PK parameters data with regards to the number of decimal places/significant digits for the listings of patient level PK parameters and summary tables of PK parameters are as follows:

PK Parameter Listings and Tables	Rounding
Derived Individual parameters	3 s f.
Directly Derived Individual parameters (e.g., C_{max} , C_{trough})	n s f. as supplied by the analytical laboratory but not more than 3 s f.
Minimum and Maximum	3 s f.
Mean/SD/Median/Geomean	3 s f.
CV%/gCV%	1 d.p.
CI	3 s f.
p-values	4 d.p.
N/n	Whole number
Exceptions for PK Tables	
t _{max} individuals and min/max	2 d.p
t _{max} median only	2 d.p

s f = significant figures, d.p. = decimal place

PK Parameter Figures:

Following figures will be created:

- Dose-normalized TCK-276 Plasma PK Parameter (dose-normalized C_{max}, all dosenormalized AUC) against Dose of TCK-276 scatter plot of individual values and line plot of geometric mean values
- Log-transformed TCK-276 PK Parameter (C_{max}, all AUCs) against the Log transformed Dose of TCK-276 based on power model
- Overlaid Individual Urinary Cumulative Excretion Rate (%) of TCK-276 versus End of Collection Interval Time Point for Day 1 and Day 7 by Dose [*Plots for Day 1 all doses and Day 7 all doses*]
- Mean (+ SD) Urinary Cumulative Excretion Rate (%) of TCK-276 versus End of Collection Interval Time Point for Day 1 and Day 7 [Plots for Day 1 all doses and Day 7 all doses]

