10.7 Appendix 7: Abbreviations and Definitions

Abbreviations	Definition
ACR	American College of Rheumatology
AE	Adverse event
AESI	Adverse event of special interest
A_e	Amount of study drug excreted unchanged in the urine
ALT	Alanine aminotransferase
AST	Aspartate aminotransferase
AUC	Area under the plasma concentration-time curve
$AUC_{0-\infty}$	Area under the plasma concentration-time curve from pre-dose (time 0) extrapolated to infinite time ($AUC_{last} + Clast/\lambda_z$) calculated using the linear-log trapezoidal rule
AUC_{0-t}	Area under the plasma concentration-time curve up to last measurable concentration
AUC_{0-24h}	Area under the plasma concentration-time curve up to 24 hours
AUC_{τ}	Area under the plasma concentration-time curve over a dosing interval, $\tau = 24$ hours
[REDACTED]	[REDACTED]
BMI	Body mass index
BP	Blood pressure
bpm	Beats per minute
CCL2	C-C motif chemokine ligand 2
CDAI	Clinical disease activity index
CDK	Cyclin dependent kinase
CFR	Code of Federal Regulations
CL/F	Apparent total body clearance
CL_r	Renal clearance
C_{max}	Maximum plasma concentration determined directly from the concentration-time profile
COMP	Cartilage oligomeric matrix protein
COVID-19	Coronavirus disease 2019
CRF	Case report forms
CRO	Contract research organization
CSR	Clinical study report

Abbreviations	Definition
MRT _{last}	Mean residence time up to last measurable concentration
MRT _{0-inf}	Mean residence time extrapolated to infinity
NOAEL	No observed adverse effect level
[REDACTED]	[REDACTED]
[REDACTED]	[REDACTED]
OTC	Over-the-counter
PD	Pharmacodynamics
[REDACTED]	[REDACTED]
PK	Pharmacokinetics
PO	By mouth
PT	Preferred term
QD	Once daily
QTc	QT interval corrected for heart rate
QTcF	QT interval corrected for heart rate using Fridericia's correction
RA	Rheumatoid arthritis
RASF	Rheumatoid arthritis synovial fibroblasts
Rb	Retinoblastoma protein
SAD	Single ascending dose
SAE	Serious adverse event
SAP	Statistical analysis plan
SARS-CoV-2	Severe acute respiratory syndrome coronavirus 2
SC	Subcutaneous
SDAI	Simplified disease activity index
SoA	Schedule of Activities
SOC	System Organ Class
SOP	Standard operating procedure
SRC	Safety Review Committee
SUSAR	Suspected unexpected serious adverse reactions
t _{max}	Time of maximum plasma concentration determined directly from the concentration-time profile
TNF	Tumor necrosis factor
t _½	Terminal elimination half-life calculated

Abbreviations	Definition
ULN	Upper limit of normal

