3.2.2 Pharmacokinetic Variables

Pharmacokinetic concentration data will be obtained at time point(s) described in the protocol version 2.0 as follows:

Blood sample for PK sample analysis to determine parent (TCK-276) and its metabolite (TEI-W00595) concentrations and for possible future metabolite assessments will be collected at the time points detailed in the Schedule of Assessments Each plasma sample will be divided into 4 aliquots (1 each for the PK, the possible future metabolite assessments, a backup for the PK, and a backup for the possible future metabolite assessments).

Blood for the PK sample analysis and for possible future metabolite assessments will be sampled at pre-dose and 0.25, 0.5, 1, 1.5, 2, 3, 4, 6, 8, 12, 16, and 24 hours (pre-dose of Day 2) after dosing on Day 1, pre-dose on Days 3, 4, 5, 6, and on 7, and 0.25, 0.5, 1, 1.5, 2, 3, 4, 6, 8, 12, 16, 24, 48, and 72 hours after dosing on Day 7. The sampling time points may be adjusted based on the PK results obtained from the previous cohorts. The last dose will be administered on Day 7.

Urine samples for the analysis of TCK-276 will be collected at the following time intervals relative to study drug dosing: 0 to 6 hours, 6 to 12 hours, 12 to 24 hours after dosing on Day 1, and from 0 (pre-dose) to 6, 6 to 12, 12 to 24, 24 to 48, and 48 to 72 hours after dosing on Day 7. Volumes of urine collected in each time window will also be recorded in the clinical database. Urine collection intervals may be adjusted based on the PK results obtained from the previous cohorts, e.g., if plasma PK sampling times are adjusted, the urine sampling times will be updated.

Derivation of PK parameters will be the responsibility of Clinical Pharmacology, Modeling and Simulation (CPMS) group,

If calculable, the following PK Day 1 parameters listed in Table 3-1 will be determined for parent, TCK-276 and metabolite, TEI-W00595, in plasma following first oral dose administration.

Parameter	WNL Name	CDISC Name	Definition
C _{max}	Cmax	CMAX	Maximum observed concentration determined directly from the concentration-time profile
DNC _{max}	CmaxD	CMAXD	Dose-normalized C _{max}
t _{max}	Tmax	TMAX	Time of maximum plasma concentration corresponding to occurrence of C_{max}
λ_z	Lambda_z	LAMZ	Terminal elimination rate constant

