4.21 Changes in the Conduct of the Study or Planned Analysis

Exploratory population definition is more elaborately defined as per study need.

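### Protocol and SAP name different trapezoidal rules for AUC0-inf; the SAP's linear rule modestly overstates Day 7 AUC0-t and AUC0-inf (about 1 to 5%) and understates Day 7 CLr

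*SAP*

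**What the plan says.** Protocol section 10.7 (Appendix 7) defines AUC0-inf as AUClast + Clast/λz, "calculated using the linear-log trapezoidal rule". This is the only place where the protocol names an integration rule. Its entry for AUC0-t reads "Area under the plasma concentration-time curve up to last measurable concentration" and names none; nor does its entry for AUCtau. Protocol 9.3.3.1 leaves further PK detail to the SAP.

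SAP 4.12.2, Table 4-1, says that AUC0-t "will be calculated by the linear trapezoidal linear interpolation rule". AUCtau is found "using the trapezoidal rule, as stated above", and AUC0-inf is AUC0-t plus Clast/λz, so all three rest on the linear rule. CLr is Ae(0-x)/AUC(0-x), "where x will be 24 (Day 1) and 72 (Day 7) hours". For Day 7 CL/F, AUCtau "will be the denominator, assuming steady state has been achieved then". Day 7 MRT0-inf is (AUMCtau + τ(AUC0-inf − AUCtau))/AUCtau.

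The late plasma samples are at "12, 16, 24, 48, and 72 hours after dosing on Day 7" (SAP 3.2.2). Terminal BLQ values are set to missing (SAP 4.12.2). SAP 4.21, where departures from the planned analysis belong, has one entry: "Exploratory population definition is more elaborately defined as per study need".

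**The concern.** AUC0-inf is a named secondary endpoint on Days 1 and 7, and the two documents compute it differently. Protocol section 9 asks for deviations from the planned analyses to be described and justified in the study report; one that is not recorded can be missed.

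The choice also has a direction. On a convex decline a straight line between two samples lies above the curve, and the error grows with the gap measured in half-lives. Day 7 has two 24 h gaps after 24 h. The same SAP table fits λz to these late points on a log scale, which treats the decline as exponential, and then joins the points by straight lines for the area. The quantities exposed are Day 7 AUC0-t, AUC0-inf, CLr and MRT0-inf, the dose-normalised AUCs and, for AUC0-t and AUC0-inf, the SAP's power model. Metabolic ratios built on these AUCs are exposed less, because errors in parent and metabolite partly cancel.

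**Working it through.** The plan states no figure for this error, so there is nothing to reproduce.

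**Inputs.** From the SAP: Day 7 times 0, 0.25, 0.5, 1, 1.5, 2, 3, 4, 6, 8, 12, 16, 24, 48 and 72 h; seven daily doses; the Table 4-1 formulas. Assumed: one compartment with first-order absorption, ka 1/h, no noise, and half-life 4 to 33 h. The upper end follows from protocol 4.3, which takes 7 days as enough for steady state: 168 h / 5 half-lives ≈ 33 h.

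**One segment.** For an exponential decline over a gap Δt, linear area / true area = (x/2)·coth(x/2), with x = ln 2 · Δt / t½. For Δt = 24 h and t½ = 8 h, x = 2.079, x/2 = 1.040 and coth(x/2) = (8 + 1)/(8 − 1) = 1.286. The ratio is 1.337, an overstatement of about 34%.

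**Whole profile.** In the same case the 24–72 h part is 13.3% of AUC0-72, and AUCtau is overstated by 0.8%. The total is about 0.133 × 33.7% + 0.867 × 0.8% ≈ 5.2%; without rounding the inputs it is 5.1%.

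**Linear-rule error on Day 7, by assumed half-life (%)**

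| Quantity | 4 h | 6 h | 8 h | 12 h | 16 h | 24 h | 33 h |
|---|---|---|---|---|---|---|---|
| AUCtau | +1.6 | +1.1 | +0.8 | +0.4 | +0.2 | +0.1 | 0.0 |
| AUC0-72 | +3.7 | +5.0 | +5.1 | +4.1 | +3.1 | +1.8 | +1.1 |
| AUC0-inf | +3.7 | +5.0 | +5.1 | +4.1 | +3.0 | +1.6 | +0.8 |
| CLr | −3.6 | −4.8 | −4.9 | −4.0 | −3.0 | −1.7 | −1.1 |
| MRT0-inf | +6.6 | +9.1 | +8.5 | +5.8 | +3.8 | +1.7 | +0.9 |

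CLr is the reciprocal effect with Ae taken as correct: at 8 h, 1/1.051 − 1 = −4.9%. MRT0-inf is hit harder because its formula multiplies the whole tail error, AUC0-inf − AUCtau, by τ.

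**Sensitivity.** Bi-exponential profiles (first-phase half-life 3 h, terminal 12 or 24 h, both assumed) give AUC0-72 +1.9 to +3.8% and CLr −1.9 to −3.6%.

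**Linear-up/log-down on the same times.** The one-compartment error is at most 0.5% in AUC0-72, AUC0-inf, CLr and MRT0-inf. In the bi-exponential profiles the AUC and CLr errors are at most 0.4%.

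**Variation with dose.** If a patient's 48 and 72 h samples are BLQ, they are set to missing and the trapezoidal error beyond 24 h vanishes for that patient. This is likelier at low doses. Illustration at t½ = 8 h: an error of +0.8% at 10 mg (last sample 24 h) and +5.1% at the top dose (last sample 72 h) shifts a two-point power-model slope by ln(1.051/1.008)/ln(17.5) = 0.0418/2.862 ≈ 0.015, using the SAP's 175 mg. The protocol's planned top dose is 150 mg; with ln(15) = 2.708 the shift is again about 0.015.

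**The case against.** The protocol names the linear-log rule once, in an abbreviation list and under AUC0-inf only, and it hands PK detail to the SAP. The linear rule is explicit, reproducible and applied alike to both days and all cohorts. With six active patients per cohort and no hypothesis test, an error of a few per cent is small.

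Most of this stands as a limit on size and scope. It does not remove the conflict. Leaving detail to the SAP lets it fill gaps, but here the protocol had already stated a rule for AUC0-inf. That rule reaches AUC0-t only because AUClast is the trapezoidal part of the definition, and the protocol gives no rule for AUCtau or AUMC.

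Three stronger readings are tempting and are not supported:

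- *The planned Day 1 to Day 7 ratios are shifted by method.* The SAP's accumulation ratios use Cmax, which needs no trapezoid, and AUCtau, which ends at 24 h on both days. In the one-compartment model the error in Racc(AUCtau) is at most 0.1%. In the bi-exponential profiles the largest difference is +0.9% on Day 7 against +1.2% on Day 1, about 0.3%. Only an informal comparison of CLr across days would move, by about 1 to 4%.
- *Exposure control or clearance is compromised.* The exposure limit and Day 7 CL/F use AUCtau, where the error is at most 1.6%. The protocol's own dose-proportionality analysis uses Cmax and AUCtau.
- *The error exceeds 100%.* The area from 24 to 72 h is overstated by about 115% at a 4 h half-life, but that area is then only 1.9% of AUC0-72.

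**Conclusion.** The concern holds as a real but minor inconsistency with a modest, one-directional bias. The documents give two rules for AUC0-inf, and SAP 4.21 is silent on it. On the planned Day 7 times the linear rule overstates AUC0-t (when the last quantifiable sample is at 72 h) and AUC0-inf by about 1 to 5%, understates CLr by about 1 to 5%, and overstates MRT0-inf by about 1 to 9%. The direction is the same in every scenario tried.

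The size rests on an assumed half-life (4 to 33 h), an assumed ka (1/h) and noise-free profiles. The documents give neither the half-life nor the LLOQ, so how many patients will have quantifiable 48 and 72 h samples is unknown. The dose-dependent effect on the power model is therefore a possibility, illustrated at about 0.015 in the slope. Nothing here changes a safety or escalation conclusion.

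**What to change.** In SAP Table 4-1, replace the linear rule with linear-up/log-down for AUC and AUMC on both days. This agrees with the protocol's linear-log definition of AUC0-inf, suits the sparse late sampling, and gives one stated rule for AUCtau and AUMC, where the protocol names none. The cost is one Phoenix setting and one SAP sentence, with no change to sampling or data collection.

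If the sponsor prefers the linear rule, add an entry to SAP 4.21 that records it as a departure from Protocol Appendix 7, gives the reason, and notes the expected direction of bias in Day 7 AUC0-t, AUC0-inf, CLr and MRT0-inf. That resolves the inconsistency but leaves the bias.

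### SAP Table 4-1 applies the terminal-slope exclusion rule to Day 7 CL/F, although Day 7 CL/F is Dose/AUCtau and contains no λz term

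*SAP*

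**What the plan says.** All of this is in SAP section 4.12.2, Table 4-1, unless noted.

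- **Exclusion rule (λz and t½ row, item 5).** The parameters covered are λz, t½, "AUC_{0-inf}, CL/F, MRT_{0-inf}, and V_z/F". CL/F carries no day qualifier. On failure they "will be flagged in listings and excluded accordingly from summary tables and statistical analysis of PK parameters".
- **Triggers.** Adjusted R² below 0.8, or a λz interval shorter than 1.3 "times the half-life and/or %AUC_{ex} is >30"%.
- **Override.** The default applies "unless otherwise determined by PK Scientist's best knowledge and judgment or if" the sponsor so instructs. No criteria are given for using it.
- **CL/F row.** Day 1 CL/F is Dose/AUC0-inf. CL/F "will be calculated similarly for Day 7 where AUC_{tau} will be the denominator, assuming steady state has been achieved then".
- **AUCtau row.** The area over the 24 h dosing interval "will be determined for multiple dose studies using the trapezoidal rule, as stated above".
- **Sampling (SAP 3.2.2).** The Day 7 profile ends with samples at "24, 48, and 72 hours after dosing on Day 7", so planned samples cover 0-24 h.
- **Not on the exclusion list.** AUCtau and DNAUCtau. Table 3-2 lists DNAUCtau for Day 7, and Table 4-1 defines it as the parameter divided by dose.
- **Minimum for a summary.** Three available values.

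**The concern.** All three triggers test the terminal regression or the extrapolation beyond the last quantifiable sample. On Day 1 they bear directly on CL/F, because AUC0-inf contains Clast/λz. On Day 7, CL/F uses the area over the dosing interval, so a poor fit through the late samples does not enter the calculation.

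Day 7 CL/F is a named secondary parameter (protocol section 3; SAP 2.2) with six active patients per cohort. Applied literally, the rule can lower its n for a reason unrelated to how it is computed. The CL/F and AUCtau rows of the same table would then rest on different patients, although one is dose divided by the other. The loss also need not be random: for a given regression window, a longer half-life makes the 1.3 half-life and 30% criteria harder to meet.

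**Working it through.** The plan states no figure on this point, so there is none to reproduce.

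**1. Formulas side by side**

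| Parameter | Formula in Table 4-1 | Contains λz or AUC0-inf? | On the item 5 list? |
|---|---|---|---|
| CL/F, Day 1 | Dose/AUC0-inf, with AUC0-inf = AUC0-t + Clast/λz | Yes | Yes |
| CL/F, Day 7 | Dose/AUCtau | No | Yes |
| AUCtau, Day 7 | trapezoidal, 0-24 h | No | No |
| DNAUCtau, Day 7 | AUCtau/Dose | No | No |
| Vz/F, Day 7 | (Dose/AUCtau)/λz | Yes | Yes |
| MRT0-inf, Day 7 | uses AUC0-inf - AUCtau | Yes | Yes |

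Only the Day 7 CL/F row is out of line. Apart from units it equals 1/DNAUCtau, so the rule can exclude a number and keep its reciprocal. Nothing elsewhere in the SAP or protocol limits item 5 to Day 1.

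**2. Illustration on the SAP's Day 7 sampling times**

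The profile is assumed: one compartment, 75 mg once daily for 7 doses, ka 1/h, t½ 12 h and V/F 1000 L. True CL/F is therefore (ln 2/12) × 1000 = 57.8 L/h. AUCtau is linear trapezoidal, and λz is fitted on the 24, 48 and 72 h samples. Only the 48 h and 72 h values were distorted.

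| Late samples | Adj. R² | λz interval (half-lives) | %AUCex | AUCtau (ng·h/mL) | CL/F = 75,000/AUCtau (L/h) | Vz/F (L) |
|---|---|---|---|---|---|---|
| Undistorted | 1.00 | 4.0 | 1.6 | 1303.2 | 57.55 | 996 |
| 48 h ×0.35, 72 h ×4 | -0.36 (fails) | 2.0 | 11.6 | 1303.2 | 57.55 | 1993 |
| 48 h ×2.2, 72 h ×8 | 0.70 (fails) | 1.0 (fails) | 30.1 (fails) | 1303.2 | 57.55 | 3985 |

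Day 7 CL/F does not change even when all three criteria fail. Day 7 Vz/F doubles and then quadruples, so it belongs on the list.

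**3. Effect on n**

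One exclusion is 1/6 = 17% of a cohort's active patients. Four exclusions leave 2, below the minimum of 3. The documents give no λz failure rate, so let p be an assumed per-patient rate, independent between patients. Then P(at least one lost) = 1 - (1-p)^6, and P(no summary) = P(Binomial(6, p) ≥ 4).

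| Assumed p | At least one Day 7 CL/F lost | Fewer than 3 remain |
|---|---|---|
| 10% | 47% | 0.1% |
| 20% | 74% | 1.7% |
| 30% | 88% | 7.1% |
| 40% | 95% | 17.9% |
| 50% | 98% | 34.4% |

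These are probabilities under the literal default, with no use of the override.

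**The case against.** The strongest reply is that almost nothing is lost, and most of it stands.

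- **The information survives.** Excluded values stay flagged in the listings. Day 7 DNAUCtau is summarised and plotted. Its geometric mean is, apart from units, the reciprocal of geometric mean CL/F, and its geometric CV% is the same.
- **Nothing downstream uses CL/F.** A reader might infer that Day 7 CL/F is the main check against Day 1 clearance. The documents do not support that: neither plans a Day 1 versus Day 7 comparison of CL/F. The planned comparison is the accumulation ratio on AUCtau and Cmax, which item 5 does not touch. Dose proportionality uses Cmax and AUCs, and escalation uses geometric mean AUCtau (protocol 7.1.2).
- **An override exists.** This is true, but it has no criteria and does not mention Day 7. SAP 4.4.3.2 places decisions on individual PK parameters after database lock. It can rescue a value but does not correct the written default.
- **The criteria are not wholly irrelevant.** Day 7 CL/F assumes steady state, and heavy extrapolation despite 72 h of sampling can signal a long half-life. Assume mono-exponential decline. Then %AUCex above 30% needs 2^(-72/t½) > 0.30, so t½ > 72 × ln 2/ln(1/0.30) ≈ 41 h. After seven daily doses AUCtau reaches at most 1 - 2^(-168/41.5) ≈ 94% of its steady-state value, so Dose/AUCtau would overstate clearance by at least about 6% (1/0.94 = 1.06). This stands as a caution. It does not justify the rule, which also fires on noisy late samples and leaves alone the accumulation ratio, which rests on the same steady-state label.
- **An incomplete 0-24 h profile is different.** Terminal values below quantification are set to missing, and the SAP does not say how AUCtau is then carried to 24 h. If λz were used for that, the criteria would bear on CL/F. The fix has to cover this case.

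**Conclusion.** The rule is wrong as written for Day 7 CL/F. By default it removes a descriptive secondary parameter on criteria that do not enter its formula, while keeping AUCtau and DNAUCtau for the same patient. This conclusion follows from Table 4-1 alone and needs no assumed failure rate. It presumes a profile that is quantifiable or bracketed to 24 h and, as the SAP itself does, steady state by Day 7.

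The consequence is modest: a smaller n in one descriptive row per cohort and, in an unlikely worst case at moderate failure rates, no row at all. The stronger reading, that valid steady-state clearances are thrown away, goes too far, because the values and their reciprocals are still reported. The point does not extend to Day 1 CL/F or to λz, t½, AUC0-inf, MRT0-inf or Vz/F on either day, where exclusion is coherent.

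**What to change.** In Table 4-1, item 5 of the λz row, replace CL/F with 'CL/F (Day 1 only)'. Add that Day 7 CL/F is included or excluded together with Day 7 AUCtau: it is reported when AUCtau comes from a profile quantifiable or bracketed to 24 h, without λz-based extrapolation. Keep λz, t½, AUC0-inf, MRT0-inf and Vz/F on the list for both days.

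The cost is one phrase and one sentence. The sentence is needed because the SAP does not currently define when AUCtau is evaluable. No new data, sampling or analysis is required. If the SAP is already final, its section 1 provides the Statistical Method Modification Form for such a change.
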